4.5. Administration of Study Medication

All randomized patients will receive study drug from Day 1 to Day 28 according to their assigned treatment and according to the randomization scheme.

Please note: Patients who remain hospitalized after 28 days of consecutive treatment with study drug are not eligible for additional treatments with study drug. Patients will receive 6 capsules in the morning and 6 capsules in the evening (ie, approximately every 12 hours, approximately at the same time every day, and at least 8 hours apart) according to their randomized treatment arm assignment as described below:

- Arm A: MP1032 (300 mg [6 × MP1032 hard gelatin capsules 50 mg] BID) for oral administration
- Arm B: 6 × placebo capsules (ie, matching MP1032 hard gelatin capsules 50 mg) BID for oral administration

In Arm A, the planned total daily dose of MP1032 is 600 mg. In Arm B, the planned total daily dose of MP1032 is 0 mg.

Study drug will be administered to each patient with water (ad libitum) for oral administration. For this study, patients should be, if possible, administered study drug in a fasted state (\geq 4 hours). However, if a patient has eaten prior to their planned administration, the dosing may proceed under a fed state. Patients may eat approximately 30 minutes postdose. The study site should record the date and time of dosing (recorded as the time when the first capsule is administered). For patients in the PK subset, study drug should be administered in fasted state on Day 1 and Day 7, when feasible. If the patient did not receive the study drug in the fasted state, then the amount of food consumed within 4 hours before dosing and 30 minutes after dose administration should be recorded and the PK samples should be collected as planned.

Any missed dose of study drug may be administered as soon as possible and the next scheduled dose may be administered according to the planned schedule as long as the doses are at least 6 to 8 hours apart. If study drug administration is interrupted for >2 days, the investigator should notify the medical monitor to determine if the study drug administration can be resumed.

Patients will be asked to abstain from the following products that may potentially affect their safety and/or the PK profile of the study drug:

- · soft or hard drugs (including cannabis) from screening and throughout the study
- smoking or using electronic cigarettes while admitted to the hospital
- consumption of alcohol-based products will be prohibited from screening until the final dose of study drug

4.6. Study Procedures and Flowchart

This document is confidential.

Page 16 of 56

Table 1:	Schedule of Assessments
----------	-------------------------

Table 1. Schedule of Assessments								
Study Period	- Ireatment Period					Follow-up Period	-	
Visit Name	Screening*	Day 1ª	Days 2 to 13	Day 14⁵	Day 21 ^b	Visit) ^b	Day 60 (Follow-up Visit) ^b / Early Study Termination after Day 28	
Study Day (window)	Day -7 to Day -1	Day 1 (NA)	Days 2 to 13 (NA)	Day 14 (±2 days)	Day 21 (±2 days)	Day 28 (±3 days)	Day 60 (±3 days)	Day of Discharge
Informed consent ^c	X	-	-	-		-	-	-
COVID-19 testing ^d	x	х	-	Xe		Xe	Xe	-
Demographics ^r	x	-	-	-		-	-	-
Medical/surgical history ⁵	x	X (updates only)	-	-		-	-	-
Inclusion/exclusion criteria	x	х	-	-		-	-	-
Complete physical examination ^h	x	-	-	-		-	-	-
Limited physical examination ^h	-	x	X (only Day 8 [±3 days]) s	X۴		χe	-	x
Vital signs ⁱ	x	Х	Xj	Xe		Xe	Xe	X
Height	X	-	-	-		-	-	-
Weight and BMI	x	х	-	Xe		Xe	Xe	x
Clinical laboratory assessments (hematology, blood biochemistry, coagulation, and urinalysis)	x	x	X (only Day 8 [±3 days]) ^s		; 14, 21, a	nd 28) ^{e, u}	-	x
ECG ^k	x	-	-	-		-	-	-
Pregnancy test (WOCBP only) ¹	x	x	-	x		-	-	X (only if discharged before Day 14 or at Early Study Termination before Day 14)
Randomization via IWRS	-	Х	-	-		-	-	-

This document is confidential.

SAP Text Version: 2.0, 31-Aug-2022 Controlled Document ID: CC , Effective Date 31-Aug-2020 Filing requirements: TMF

Page 17 of 56

Study Period	Screening Period		Treatment Period				Follow-up Period	-
Visit Name	Screening ^a	Day 1ª	Days 2 to 13	Day 14 ⁶	Day 21⁵	Day 28 (End of Treatment Visit) ^b	Day 60 (Follow-up Visit) ^b / Early Study Termination after Day 28	Day of Discharge / Early Study Termination before Day 28
Study Day (window)	Day -7 to Day -1	Day 1 (NA)	Days 2 to 13 (NA)	Day 14 (±2 days)	Day 21 (±2 days)	Day 28 (±3 days)	Day 60 (±3 days)	Day of Discharge
Retrieve the 14-day blinded study drug kit via the study drug kit number assigned by IWRS		x		X ^v				X (only if discharged before Day 14; NA for Early Study Termination)
Blood sample collection for biomarkers	-	X٥	X (only Day 7)°	X (Days 14, 21, and 28)°			Xe'o	-
Administer blinded study drug BID	-			Xt			-	-
Provide remainder of the assigned blinded study drug kit(s) to the patient along with instructions ^m	-	-	-	-		-	-	X (only if discharged during the treatment period; NA for Early Study Termination)
Provide patient with the diary and train patient on use of the diary ^m	-	-	-	-		-	-	X (only if discharged during the treatment period; NA for Early Study Termination)
COVID-19 symptoms	X	Х	-	X		x	x	x
COVID-19 severity ^p	x	х	-	-		-	-	-
Clinical status related to COVID-19 on the NIAID 8-point ordinal scale ^q	x	x	x	x		x	x	x
EQ-5D-5L questionnaire ^r	-	-	-	-		-	x	X (only if discharged/ early terminated

This document is confidential.

SAP Text Version: 2.0, 31-Aug-2022 Controlled Document ID: CC , Effective Date 31-Aug-2020 Filing requirements: TMF

Page 18 of 56

Study Period	Screening Period		Treatment Period				Follow-up Period	-
Visit Name	Screening ^a	Day 1ª	Days 2 to 13	Day 14⁵	Day 21⁵	Day 28 (End of Treatment Visit) ^b	Day 60 (Follow-up Visit) ^b / Early Study Termination after Day 28	
Study Day (window)	Day -7 to Day -1	Day 1 (NA)	Days 2 to 13 (NA)	Day 14 (±2 days)	Day 21 (±2 days)	Day 28 (±3 days)	Day 60 (±3 days)	Day of Discharge
								before Day 60)
Blood sample collection (plasma) for PK (from the PK subset of approximately 30 patients who give optional consent) ⁿ	-	x	X (only Day 7) ^j			-	-	-
AEs		х						
Prior and concomitant medications		x						

Abbreviations: AE = adverse event; BID = twice daily; BMI = body mass index; COVID-19 = coronavirus 2019; ECG = electrocardiogram; eCRF = electronic case report form; EQ-5D-5L = EuroQol-5D-5L; IEC = independent ethics committee; ICU = intensive care unit; IRB = institutional review board; IWRS = interactive web-response system; LAR = legally authorized representative; NA = not applicable; NIAID = National Institute of Allergy and Infectious Diseases; PK = pharmacokinetic; RT-PCR = reverse transcription-polymerase chain reaction; SAE = serious adverse event; SARS-CoV-2 = severe acute respiratory syndrome coronavirus type 2; SoC = standard of care; SpO₂ = saturation of oxygen; WOCBP = women of childbearing potential

- a. Those patients who are fully eligible (all screening assessments are available) can have Day 1 performed on the same day as screening. If screening and Day 1 are performed on the same day, visit procedures required for both visits do not need to be repeated.

- d. At the screening visit, the local laboratory may perform COVID-19 testing by standard RT-PCR assay or equivalent test. At screening, a positive test must be available in order for the patient to be randomized on Day 1. If the patient has a previous confirmation of SARS-CoV-2 (within 7 days of Day 1), the SARS-CoV-2 test at screening is not required. On Day 1, Day 14, Day 28, and Day 60, samples will be sent to the central laboratory for COVID-19 testing by standard RT-PCR assay. The result of the COVID-19 tests (positive/negative) must be documented in the eCRF. Further details will be described in the laboratory manual. Please note: If COVID-19 tests are performed at unscheduled time points (eg, according to SoC), findings (ie, positive/negative result) must be recorded in the eCRF.
- e. Not all assessments will be able to be performed if the Day 14, Day 28, and/or 60 visits are conducted via a telephone/virtual call (the patient's caregiver may assist during the telephone/virtual call). If the assessment can be conducted via a telephone/virtual call, the study site should record the details; otherwise, the missed assessment will not be considered a protocol deviation. If the visit is conducted by a home healthcare nurse, these assessments should be conducted, if possible; if the assessment can be conducted via home healthcare nurse, the study site should record the details; otherwise, the missed assessment will not be considered a protocol deviation. If the visit is conducted via home healthcare nurse, the study site should record the details; otherwise, the missed assessment will not be considered a protocol deviation. These assessments must be conducted if the visit is conducted at the study site. All efforts should be made to collect clinical laboratory assessments on Day 14 (± 2 days) and Day 28 (± 3 days). Please note: In cases in which the patient is deemed lost to follow-up, the investigator or designee must make every effort to regain contact with the patient (eg, telephone calls, letter to the patient's last known mailing address, or local equivalent methods). In cases where the patient's LAR provides informed consent on behalf of the patient, the study site should attempt to contact the LAR. Additionally, the study site should attempt to regain contact with the patient using the alternative contact information provided by the patient/LAR at the time of informed consent. These contact attempts must be documented in the patient's medical records.
- f. Demographics will include sex, age, race, and/or ethnicity.
- g. Medical/surgical medical history includes all active and chronic diseases (eg, asthma and COPD), and any diseases diagnosed in the past 1 year (before screening) that the investigator considers clinically significant. Additional pre-existing conditions present at the time when informed consent is given and up to the time of first dosing (Day 1) are to be regarded as concomitant. Medical history will include documentation of social behaviors, including use of tobacco, nicotine (including use of electronic cigarettes), and soft or hard drugs (including cannabis), as well as alcohol consumption, if applicable. Smoking history also must be documented as part of medical history and includes: never, light (<100 cigarettes/lifetime), active smoker, and former smoker (quit date). History of number packs/day, number of smoking years, and quitting time for former and active smokers must also be documented. Additionally, the investigators will document at screening the patient's Charlson score via the Charlson Comorbidity Index (see Section 12.1 of protocol for further details).

- h. A complete physical examination will be performed at screening. Physical examinations will be performed by a physician, nurse, or other appropriately trained staff. The complete physical examination includes: head, eyes, ears, nose, and throat; heart; lungs; abdomen; skin; cervical and axillary lymph nodes; and neurological and musculoskeletal systems. A limited physical examination to verify continued patient eligibility and to follow-up regarding any change in medical history will be performed at the visits indicated above. Symptom-driven, limited physical examinations may be performed as clinically indicated during the study (according to SoC).
- i. Vital signs include systolic and diastolic blood pressure, heart rate, respiration rate, SpO₂, and body temperature. All vital signs will be measured after the patient has been resting for at least 5 minutes. Blood pressure measurements are to be taken in the same arm for the duration of the study. Moreover, additional vital signs may be performed as needed in case of any cardiac AE.
- j. For patients who remain hospitalized only.
- k. A 12-lead, resting ECG will be obtained locally at screening. At screening, the investigator must examine the ECG traces for clinically significant abnormalities that could exclude the patient from the study. ECGs should always be obtained in supine position after adequate rest (≥5 minutes).

This document is confidential.

SAP Text Version: 2.0, 31-Aug-2022 Controlled Document ID: CCC , Effective Date 31-Aug-2020 Filing requirements: TMF

Page 20 of 56

- 1. For WOCBP, a serum sample for pregnancy testing must be collected at screening and a urine sample for pregnancy testing must be collected before the first dose on Day 1. Pregnancy tests must be negative for the patient to be randomized and treated. A urine pregnancy test will be repeated on Day 14 (± 7 days). If the patient is discharged before Day 14, urine pregnancy test at day of discharge should be done, and urine pregnancy test at Day 14 is not required. If the patient is discharge after Day 14, urine pregnancy test at day of discharge is not required test should be done at Day 14, and urine pregnancy test at day of discharge is not required (whichever comes first). Patients with a positive pregnancy test will be discontinued from study drug.
- m. Only for patients discharged before Day 28. If the patient does not feel comfortable to complete the diary, the site will alternatively provide the patient with the option to be called, twice a day, to confirm that the study drug is taken as instructed.
- n. Plasma PK samples will be collected via sparse sampling from approximately 30 patients (who give optional consent) in a 2:1 ratio to assess the PK of MP1032 on Day 1 (single dose) and Day 7 (steady state). A total of 16 samples will be collected relative to the first dose on Day 1 and the first dose on Day 7. Samples on Day 1 and Day 17 will be collected predose (within 10 minutes before the first daily dose) and postdose at 10 minutes, 20 minutes, 30 minutes, 60 minutes, 120 minutes, 8 hours (before next dose), and 24 hours before the next morning dose (if applicable), if possible. Patients who provide consent for the PK sampling, but are no longer hospitalized on Day 7, will not have Day 7 PK samples collected.
- o. Blood samples to be obtained on Day 1 (before the first study drug administration) and Days 7, 14, 21, 28, and 60 (when possible). Blood samples for biomarkers must be collected on Days 7, 14, 21, 28, and 60 if a patient is still hospitalized. If a patient is discharged, the study site should arrange an outpatient visit (ie, at the study site) to accommodate the collection of blood samples for biomarkers on Days 7, 14, 21, 28, and 60.
- p. To standardize the assessment of COVID-19 severity, respiratory rate, SpO₂, and heart rate will be measured when the patient is on room air at sea level (ie, no supplemental oxygen, if possible) and at rest for at least 5 minutes. If possible, the site should collect the information from each patient at the same time each day (±1 hour).
- q. Record the patient's clinical status related to COVID-19 on the NIAID 8-point ordinal scale and also record the date and time for each individual component of the NIAID 8-point ordinal scale including: invasive or non-invasive mechanical ventilation/ECMO start/stop, high-flow/mask oxygen start/stop, supplemental oxygen start/stop (nasal cannula, liter flow [and its conversion to FiO₂], other delivery services), hospital discharge (whether with limitations or without limitations), hospitalization type (eg, transfer to ICU) start/stop, and (if applicable) death, cause of death (including relatedness to COVID-19), and date/time of death. If possible, the site should collect the information from each patient at the same time each day (±1 hour).
- r. The EQ-5D-5L (Appendix 2 of protocol) is only required for discharged patients and at the following visits: day of discharge, Day 60, and Early Termination visit (if applicable). The EQ-5D-5L is not required for patients who remain hospitalized until study end.
- s. The limited physical examination and clinical laboratory assessments on Day 8 (± 3 days) will be collected in all patients who remain hospitalized. If the patient is discharged before Day 8 (± 3 days), the site should arrange to have the physician assess the patient via a telephone/virtual call. If the physician determines during the telephone/virtual call that the limited physical examination and clinical laboratory assessments are clinically indicated, then the site should arrange for an outpatient visit to collect these assessments.
- t. For all patients (except on Day 1 and Day 7 for patients in the PK subset): Patients should not eat within the 30 minutes before planned study drug administration and within the 30 minutes after study drug dosing, when feasible. However, if a patient has eaten within the 30 minutes before their planned study drug administration, study drug dosing may proceed. The study site should record the date and time of dosing (recorded as the time when the first capsule is administered). For patients in the PK subset on Day 1 and Day 7 only: Patients should not eat within the 4 hours before planned study drug administration and within the 120 minutes after study drug dosing, when feasible. Thus, study drug should be administered in fasted state (≥ 4 hours), when feasible. However, if a patient has eaten within the 4 hours before their planned administration, study drug dosing may proceed. The patient's fed or fasted state, as well as food intake (yes/no) within the 120 minutes after study drug dosing should be recorded. The PK samples should be collected as planned regardless of the patients' fasted/fed state. The study site should record the date and time of dosing (recorded as the time when the first capsule is administered).

This document is confidential.

SAP Text Version: 2.0, 31-Aug-2022 Controlled Document ID: COMPANY, Effective Date 31-Aug-2020 Filing requirements: TMF

Page 21 of 56

- u. The clinical laboratory assessments on Day 21 will be collected in all patients who remain hospitalized. If the patient is discharged before Day 21, the site should arrange to have the physician assess the patient via a telephone/virtual call. If the physician determines during the telephone/virtual call that the clinical laboratory assessments are clinically indicated, then the site should arrange for an outpatient visit to collect this assessment.
- v. The +2 day window does not apply to the retrieval of the 14-day blinded study drug kit as the second kit must be distributed at the latest on Day 14.

This document is confidential.

Page 22 of 56

5. Endpoints

5.1. Primary Efficacy Endpoint

The primary efficacy endpoint of this study is:

Proportion of patients with disease progression on Day 14. Disease progression is defined as the
proportion of patients who are not alive or who have respiratory failure. Respiratory failure is defined
as patients who have a score of 2, 3 or 4 on the National Institute of Allergy and Infectious Diseases
(NIAID) 8-point ordinal scale (see below).

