3.1. Primary Objective

 To measure the effect of MP1032 plus standard of care (SoC) versus placebo plus SoC on Day 14 on disease progression in patients with moderate to severe coronavirus disease 2019 (COVID-19)

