4.3. Determination of Sample Size

The primary efficacy endpoint 'proportion of patients with disease progression on Day 14' is assumed to be 10% in the 300 mg MP1032 BID plus SoC treatment group (Arm A) and 30% in the placebo plus SoC treatment group (Arm B). Using the Chi-square test with type I error alpha=10% two-sided for this proof-of-concept study and 2:1 randomization ratio, 114 patients (76 in Arm A and 38 in Arm B) are required to achieve a statistical power of 83%. Considering about 5% early study terminations, the necessary sample size for randomization results in 120 patients in total (80 in Arm A and 40 in Arm B). If during the conduct of the study the early study termination rate is higher than the estimated 5%, then an increase in the randomized number of patients may be necessary.

Sample size estimation is performed using nQuery 8, Version 8.6.1.0.

A subset of randomized patients will be consented for the collection of blood samples for PK measurements. The PK subset consists of approximately 20 patients from the 300 mg MP1032 BID plus SoC group and approximately 10 patients from the placebo plus SoC group, up to a total of approximately 30 patients.

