5.3. Other Secondary Efficacy Endpoints

The other secondary efficacy endpoints of this study are:

This document is confidential.

SAP Text Version: 2.0, 31-Aug-2022 Controlled Document ID: CCC , Effective Date 31-Aug-2020 Filing requirements: TMF

Page 23 of 56

- Proportion of patients with disease resolution on Day 14. Disease resolution is defined as patients who are alive and have a score of 6, 7, or 8 on the NIAID 8-point ordinal scale (as listed above).
- All-cause mortality rate at Day 14 and Day 60
- Change of clinical status related to COVID-19 on Day 14 compared with baseline according to the NIAID 8-point ordinal scale (as listed above)
- Proportion of patients requiring invasive ventilation (mechanical ventilator and/or ECMO), or who
 are not alive on Day 14 or Day 28
- · Proportion of patients in each category of the NIAID 8-point ordinal scale
- Time to (first) improvement of at least 1 category on the NIAID 8-point ordinal scale (until Day 28).
 Patients who did not improve at least 1 category on the NIAID scale or deaths before Day 28 will be censored at Day 28.
- The odds ratio between MP1032 and SoC and placebo and SoC of the number of patients with clinical status improvement from baseline on the NIAID 8-point ordinal scale (ie, an improvement of at least 1 category) at Day 14 and Day 28
- Total duration of hospitalization (from baseline to discharge; with death censored on the last day of the observed period – at Day 28 or Day 60, respectively)
- Proportion of patients alive and testing negative for COVID-19 on Day 14, Day 28 and Day 60

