10.1. Primary Efficacy Estimands and Analysis

The main estimand and the second estimand for the primary efficacy endpoint that is defined as a binary variable indicating disease progression (death or respiratory failure) at Day 14 will be compared between the treatment groups based on the common risk difference resulting from the MH test considering the 4 strata out of the combinations of the 2 randomization stratification factors disease severity (moderate versus severe) and age-class (\leq 65 years versus >65 years).

Missing data on Day 14 resulting from study termination prior to Day 14 are not expected. However, in case they happen, such monotone missings will be imputed by multiple imputation using information from similar patients of the same treatment group assuming the missings are MAR. Missing post-baseline data for patients randomized but not treated will be imputed by BOCF. Intermediate missing data of Day 14 (ie, NIAID assessments prior Day 14 and at Day 28 are available, but only Day 14 is missing) will be imputed by LOCF. The comparison between the treatment groups will be performed on the ITT after imputation of missing values using the MH test. 95% confidence interval (CI) will be performed by imputation of missing values at Day 14 with 'progression' assuming that missings happen not at random (MNAR). A table with number and type/reason of missing values in the primary efficacy variable will be provided by treatment group on the ITT.

All above described analyses will be repeated on PPS as supportive analysis. Additionally a logistic regression model with treatment and the 2 stratification factors as covariables will be applied on the ITT as supportive analysis.

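### The primary endpoint is an absolute Day 14 state labelled progression, and its analyses leave out the baseline NIAID score, at some cost in precision and clarity but without bias

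*SAP*

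**What the plan says.** The primary objective (SAP 3.1) is "To measure the effect of MP1032 plus standard of care (SoC) versus placebo plus SoC on Day 14 on disease progression" in moderate to severe COVID-19. Section 5.1 turns this into death or respiratory failure on Day 14, the latter defined "as patients who have a score of 2, 3 or 4 on the National Institute of Allergy and Infectious Diseases" scale. Section 5.2 uses the same definition on Day 28 for key secondary endpoint 1. On that scale lower is worse, and 4 means in hospital on supplemental oxygen. A note in 5.2 makes one exception: a patient who needed oxygen before COVID-19 and is back at that level is treated as not requiring it.

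The primary analysis (7.1, 10.1) is a Mantel-Haenszel risk difference over four strata, severity by age class. Section 10.1 continues: "Additionally a logistic regression model with treatment and the 2 stratification factors as covariables will be applied on the ITT as supportive analysis". Sections 7.2, 7.3, 10.2.1 and 10.2.2, with the closing paragraph of 10.2.4, give key secondary endpoints 1 and 2 the same pair of analyses.

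Baseline NIAID is recorded at screening and Day 1 (Table 1). It is a covariate in the ANCOVA for key secondary endpoint 4 (7.5, 10.2.4) and in the similar Day 14 model (10.3), and it is tabulated by arm (9.4). It is not among the subgroups in 8.6.

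**The concern.** The label speaks of change, while the definition speaks of a state. A lower risk in Arm A could mean that fewer patients got worse, or that more patients already on oxygen came off it by Day 14. Both are worth knowing, but they are different claims, and no planned analysis of the primary endpoint separates them.

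For an outcome read off the same scale, the entry score is also the natural prognostic covariate. Leaving it out gives up precision in a trial with 40 placebo patients. It also leaves chance differences between arms in entry oxygen need unadjusted, except as far as the severity stratum captures them.

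**Working it through.** **1. The plan's own figure.** Inputs from SAP 4.3: the event proportion "is assumed to be 10% in the 300 mg MP1032 BID plus SoC treatment group (Arm A) and 30% in the placebo plus SoC" group; "Using the Chi-square test with type I error alpha=10% two-sided for this proof-of-concept study and 2:1 randomization ratio"; 76 and 38 evaluable patients.

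- Pooled rate: (76 × 0.10 + 38 × 0.30)/114 = 19/114 = 0.1667.
- SE under the null: √[0.1667 × 0.8333 × (1/76 + 1/38)] = 0.0740.
- SE under the alternative: √(0.10 × 0.90/76 + 0.30 × 0.70/38) = 0.0819.
- z = (0.20 − 1.645 × 0.0740)/0.0819 = 0.955, so power is 83.0%.
- Randomised: 114/0.95 = 120.

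The stated design reproduces.

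**2. Which patients count as events.** Severe disease in 4.1 includes low SpO2, PaO2/FiO2 below 300 and ARDS, and nothing in the SAP keeps score 4 out at entry. A patient who goes from 4 to 4 is therefore an event, subject to the exception in 5.2. The imputation rule shows the same thing. A patient randomised but never treated, with no later data, receives the baseline value (7.1), so an entry score of 4 becomes progression with no follow-up at all.

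**3. Severity as a stand-in for entry score.** Severe status in 4.1 can rest on respiratory rate or heart rate, neither of which implies oxygen use. Patients on long-term oxygen are classed as severe, yet a return to prior use counts as not requiring oxygen. The stratum therefore overlaps with entry score but does not replace it.

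**4. How strongly entry score could predict the outcome.** The SAP gives neither the share on oxygen at baseline (q) nor the risk by entry score, so both are assumed here. With 30% placebo risk overall and risk b in patients not on oxygen, the risk in those on oxygen is [0.30 − (1 − q)b]/q:

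| q | b = 5% | b = 10% |
|---|---|---|
| 0.5 | 55% | 50% |
| 0.7 | 41% | 39% |
| 0.9 | 33% | 32% |

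Entry score can be a strong predictor, yet 45% to 68% of placebo patients on oxygen at entry would still be non-events.

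**5. What the omission costs.** Simulation of the Mantel-Haenszel risk difference (Sato variance): 114 patients, blocked 2:1 within the four strata, two-sided alpha 10%, 2,000 trials per row. Assumed: 30% of patients in the older age class, risks set to give 30% v 10% overall, and one odds ratio in all patients. The last column adds baseline oxygen status (4 or lower v 5) to the strata.

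| On oxygen: severe / moderate | Share severe | Risk if not on oxygen | Power, 4 strata | Power, oxygen status added |
|---|---|---|---|---|
| 100% / 0% | 50% | 3% | 88.5% | 88.5% |
| 100% / 0% | 50% | 8% | 85.2% | 85.2% |
| 90% / 30% | 50% | 3% | 83.2% | 84.5% |
| 90% / 30% | 50% | 8% | 81.2% | 82.0% |
| 70% / 30% | 70% | 3% | 79.9% | 84.4% |
| 70% / 30% | 70% | 8% | 81.9% | 83.9% |
| 60% / 60% | 70% | 3% | 80.6% | 84.9% |
| 60% / 60% | 70% | 8% | 80.2% | 83.1% |

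The simulation error of one power figure is about √(0.82 × 0.18/2000) = 0.9 points. The gain is zero where severity and oxygen status coincide, and about 1 to 4.5 points elsewhere. The mean risk difference is −0.20 in every row with or without the extra factor, and rejection under no effect is about 9% to 12% either way. These runs add a stratum. The standardised logistic estimate proposed below uses the same information but was not itself simulated.

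**The case against.** The definition is open. Section 10.1 itself glosses the endpoint as death or respiratory failure, a fixed-day state is a legitimate endpoint, and the objective uses the term that 5.1 defines. Adjusting only for the stratification factors is defensible, and severity is already in the randomisation, the strata, the logistic model and the subgroups. Results relative to baseline are planned on the same scale and day: the covariate-adjusted Day 14 change (10.3), and the odds ratio for "clinical status improvement from baseline on the NIAID 8-point ordinal scale" (5.3). All of this stands, and it keeps the point modest. It does not supply a primary-endpoint analysis that uses the entry score.

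Three stronger readings are tempting.

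- **Improvement counted as progression.** A reader might infer that a patient moving from 3 to 4 is both progressed and improved. The wording allows it, but it needs entry at score 2 or 3. The SAP excludes critical disease without giving the criteria, so it does not show that such patients are enrolled.
- **Entry score largely determines the outcome.** If 60% enter on oxygen with placebo risks of 45% v 7.5%, then 0.6 × 0.45/0.30 = 90% of placebo events come from them. Those inputs are not in the SAP, and even then 55% of these patients are non-events.
- **Imbalance distorts the result.** On the same inputs, one SE of imbalance is √[0.6 × 0.4 × (1/80 + 1/40)] = 9.5 points, which times 0.375 gives 3.6 points of risk difference. This ignores stratification by severity and applies the placebo slope to both arms. With Arm A risks of 15% and 2.5% it is √[0.24 × (0.125²/80 + 0.375²/40)] = 3.0 points, still before stratification. Either way it is sampling variation that the confidence interval covers, not bias.

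The remedy also has a cost. On those inputs, patients not on oxygen yield 32 × 0.025 + 16 × 0.075 = 2 expected events, with a chance of none of 0.975³² × 0.925¹⁶ = 13%. An ordinary logistic fit could then separate.

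**Conclusion.** The point holds as one of precision and interpretation. The primary endpoint and key secondary endpoint 1 count an unchanged score of 4 as progression, apart from prior oxygen users back at their usual level. The analyses of these two endpoints and of key secondary endpoint 2 omit a baseline value that the trial collects and uses elsewhere.

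The loss is about 0 to 4.5 points of power. That range rests on 50% to 60% of patients on oxygen at entry, placebo risks of 3% to 8% without oxygen and 45% to 57% with it, and the severity-oxygen overlaps tabulated above. None of these figures is in the SAP. A reader should not infer that the randomised comparison is biased, or that the sample size or the 83% power is wrong.

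**What to change.** 1. In the logistic models of 10.1 and the closing paragraph of 10.2.4, add baseline NIAID (4 or lower v 5 or higher) for the primary endpoint and key secondary endpoints 1 and 2. Report the standardised risk difference with its confidence interval. Name a penalised (Firth) fit in advance for use if sparse events cause separation.
2. Add a supplementary analysis of death or a Day 14 score below baseline, with its own estimand. It is a different variable, so it should not be presented as a sensitivity analysis of the primary one.
3. Describe the primary result as death or respiratory failure (NIAID 2-4) at Day 14.

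The cost is SAP wording, one model term and one extra table, settled before unblinding. If the protocol does not foresee these analyses, section 16, which now declares no changes, needs an entry. The endpoint definition, the Mantel-Haenszel primary analysis, the sample size and the data collection stay as they are.
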